specialists, and school members to evaluate *Adoption*. We will conduct a survey of providers and school staff following the intervention to gauge their reaction to the intervention components and their willingness to support them in the future. To assess *Implementation* we will use check-lists, tracking logs, surveys and chart reviews to measure the extent to which participants partook in each program component (telemedicine visits, guideline-based adjustments, % medication doses delivered at school, and/or through video supported DOT). To assess *Maintenance* we will use surveys and open-ended questions to evaluate plans for continuation (or modification) of each intervention component post-study, and we will use 12-month follow-up data to analyze long-term effects on primary outcomes and QOL.

COVID-19

In response to the COVID-19 pandemic, we will follow the Human Subjects Research guidelines outlined by the University of Rochester to continue enrollment for this study. Please find the following link for these guidelines: <https://www.urmc.rochester.edu/coronavirus/coronavirus-research/guidance-for-researchers/human-subjects-research.aspx>. We will minimize in-person contacts to only those tasks necessary to conduct the research (e.g., obtaining consent, review medications and forms). We will ensure that team members are appropriately trained in safety measures, maintain social distancing when possible, use personal protective equipment for themselves and research subjects (and family members), and will ensure proper cleaning/sanitizing of hands, equipment and workstations. We will continue to monitor and follow the updated guidelines put forth by the UofR in the link above.

The intervention may look different during the COVID-19 pandemic. If schools are open, participants in the Intervention group may receive directly observed therapy (DOT) of their preventive asthma medication supervised by the school nurse or health aide. Additionally, they may receive telemedicine visits at school. However, if schools are not fully open or by family preference, we will support families with ongoing medication adherence, which will include school-based and/or video supported DOT. Additionally, providers may conduct telemedicine visits without the data obtained by clinical telehealth assistants onsite using Zoom or another HIPAA compliant method to remotely connect with families.

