For all enrolled children, we will contact the PCP by facsimile or email and will recommend preventive asthma medication as well as a referral to an asthma specialist. We will encourage the use of pharmacies with delivery (several local pharmacies routinely provide delivery services) with instructions indicating one canister of preventive medication, with a spacer and mask as appropriate, to be dispensed for home doses on weekends and days the child does not attend school, and a second canister for supervised medication administration at school on school days if needed. This system has been successful >95% of the time in our prior studies. We include the recommendation for daily preventive medication for all children, including those in the EC group, because we have established the effectiveness of consistent preventive medication use in our prior studies and it is well accepted as a care measure nationally. The specialist referral is consistent with guideline recommendations for children with this level of severity.

TEAM-UP Intervention:

Children randomly assigned to TEAM-UP will have a telemedicine assisted specialist visit scheduled after 4 weeks of initiating school-based and/or video supported DOT, as well as 2 subsequent follow-up visits. The visits will be performed by a specialist in pediatric asthma. Appointments will be scheduled in conjunction with the child's caregiver. If the visit is able to be prepared at school, health data will be collected by clinical telemedicine assistants (CTAs) who already work in the district. In these instances the CTA will bring the mobile telemedicine unit and meet with the child at school. If conditions allow, the CTA will obtain spirometry and FeNO readings, and then enter information regarding symptoms and triggers (collected at screening) into the system. Physical examination data will be uploaded (medical images, height/weight, breath sounds). Visits will either be conducted in real time using videoconferencing or information will be securely stored in the telemedicine system's "virtual waiting room" until a provider is ready to complete the visit.

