Any new medications that are prescribed will be sent to pharmacies that routinely provide delivery services. Children will receive one medication dose daily through school if this is possible;⁵⁹ additional needed doses will be given at home by caregivers and adherence will be video supported. While many schools do not have a full time nurse, schools are prepared for daily medication administration when in session for in-person learning. In our prior study, medications were administered >95% of the time children were in school. All children will be instructed to rinse their mouth with water after each medication dose. Medication administration logs (school-based and/or video supported DOT) will be used for tracking.

A telemedicine visit summary will be sent to the PCP, with requests for feedback and input, and the PCP will continue to coordinate the care. The 3 major practices serving urban children in Rochester are certified as Patient Centered Medical Homes, and include care coordinators to assess barriers and facilitate access to services. Maintaining care through this system is critical to ensure continuity and unification of services. A visit summary and AAP will also be sent to the caregiver.

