Follow-Up Telemedicine Asthma Control Assessments – Follow-up specialist-directed telemedicine assessments will occur twice during the study period; 4-6 weeks after the initial telemedicine visit, and again 4-6 weeks later. These visits will focus on further evaluation of symptoms to ensure the goals of therapy are being met, assessment of triggers or co-morbid conditions that might interfere with an optimal response to treatment, and continued asthma education. Medication optimization will again be considered as needed. The specialist will also assess for medication-related side effects (oral thrush, growth monitoring). Further, many of these children will have allergic asthma and may benefit from initiation of antihistamine medications, specific allergy testing, and possibly the use of a biologic medication (Omalizumab or Meplizumab). If allergy testing or a biologic medication are needed, an in-person visit will be recommended (allergy/laboratory testing cannot be feasibly conducted in schools). If a possible co-morbid condition is identified, visits for additional evaluation (i.e.; sleep studies, upper GI evaluation, etc.) will be scheduled. The specialist may also refer to community resources as needed (i.e.; Healthy Home Partnership for trigger assessment, New York State quit line for smoking cessation support, care coordination from the medical home for transportation assistance). Information regarding any changes in the regimen will be sent to the PCP through the telemedicine system.

Children who continue to have poor control at the final telemedicine visit will be referred for an in-person specialist visit for further evaluation and management. These visits will be facilitated as needed with the support of the child's PCP and medical home. We do not anticipate the opportunity to step-down therapy, since all children will have moderate to severe persistent symptoms at the start of the trial and guidelines recommend several months of optimal anti-inflammatory therapy. A natural time for discontinuing or stepping-down therapy occurs at the end of the school year when the children will no longer be receiving medications through school and/or video supported DOT. Approximately, two weeks prior to the close of the school year, we will notify specialist providers, PCPs and families that children receiving preventive medications at school no longer will receive medications through the study.

Monitoring for Treatment Fidelity:

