The study team nurse will review telemedicine visit records after each visit to ensure completion by the specialist provider within 3 days, and to assess delivery of guideline-based care. Any concerns will be relayed back to the specialist provider. We will track delivery of medications, DOT, and show rates at needed in-person visits. We will also ensure ongoing communication with the PCP.

Subgroup of Teens

For a small subgroup (approximately 10-30 teens), we will test the feasibility of conducting the TEAM-UP intervention with teens. This subgroup will not be randomized. For all teens, we will initiate a telemedicine visit conducted within the school (or home) with an asthma specialist. Two follow-up visits will occur either with an asthma specialist or with an asthma nurse educator, to re-assess symptoms and ensure guideline-based care is implemented appropriately. As routine within the Telemedicine Program, the teen's PCP will be notified of all visits, severity of child as documented within the telemedicine visits, and any changes in care that are recommended through this program. Unlike the study for younger children, we will not implement DOT of medications as part of the program for teens, although the telemedicine provider may suggest DOT in their asthma care recommendations.

Enhanced Care (EC) Comparison Condition:

Similar to the TEAM-UP group, children in the EC group will receive a symptom assessment and asthma education materials at baseline, and we will contact the PCP by facsimile or email and will recommend daily preventive asthma medication as well as a referral to specialist. However specialist visits will not be facilitated through the study. We will also give providers a summary of the national asthma guidelines and a list of community resources including the Healthy Homes Partnership and the New York State quitline. We will provide systematic reminders to the family and PCPs to schedule recommended healthcare visits at the same intervals as the TEAM-UP group's telemedicine visits. Participants will not be blinded to group allocation; they will be told that they are randomly assigned to 2 different ways of approaching asthma management. In all of our prior studies, the EC group improved over time, creating a conservative bias.

Follow-Up Assessments:

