We will also consider whether certain process measures from our conceptual framework (guideline-based corrective actions, adherence, patient/provider communication, satisfaction with care) act as mediators in the relationship between the intervention and outcomes.⁷² Thus we will estimate both the direct intervention effect on outcomes, as well as the indirect effect through mediators. For each purported mediator, we will use structural equation models (SEM)⁷³ to model its relationship to treatment and primary outcome. Maximum Likelihood (ML) will be used for estimation. Goodness-of-fit will be assessed in a two-level process. In the first level, the fit of the unrestricted model will be tested using standard diagnostic measures for linear regression. In level two, the appropriateness of assumption of the proposed structural equation model will be investigated by testing this model against the unrestricted model. The following indicators will be used:⁷⁴ (a) Comparative Fit Index (CFI), (b) Non-Normed Fit Index and (c) Root Mean Square Error of Approximation.⁷⁵ We will use chi-square statistics for the structural invariance tests to determine effect modifiers. These analyses will aid in our understanding of pathways by which TEAM-UP impacts outcomes.

The primary analyses will include all randomized subjects. Substantial attention will be invested in participant retention; reasons for any withdrawals that may occur will be documented. Missing data patterns will be examined by comparing subjects who discontinued with those who remained in the study. Inference based on the proposed methods GEE and/or LMM is valid provided that missing data follows the missing completely at random (MCAR) assumption. However, if the occurrence of missing data depends on the observed response but is independent of unobserved data (MAR), weight GEE (WGEE) will be used. Sensitivity analysis to the MAR assumption will also be carried out by modeling the between-group difference using WGEE.^{76,77} Separate secondary per protocol analyses will be performed and interpreted with caution.

Cost Effectiveness Analysis:

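### The supportive mediation model does not adjust the corrective-action path for asthma control before the action, so the effect of step-ups on SFD is open to confounding by indication

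*Combined protocol and SAP*

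**What the plan says.** **The mediation analysis.** The Primary Analysis section introduces it as supportive: "We will also consider whether certain process measures from our conceptual framework" act as mediators. The first measure listed is guideline-based corrective actions, which objective 6 defines to include step-wise medication adjustments and the identification and treatment of allergies and co-morbid conditions. Each mediator gets a structural equation model "to model its relationship to treatment and primary outcome". No covariate is named. Baseline SFD is a named covariate only for the primary linear mixed model.

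**What prompts an action.** The Background calls for a further step-up when asthma stays uncontrolled. The follow-up visits, held "4-6 weeks after the initial telemedicine visit, and again 4-6 weeks later", consider medication changes as needed. "Children who continue to have poor control at the final telemedicine visit will be referred" for an in-person specialist visit.

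**What is recorded at the visits.** At school-prepared visits the assistant takes spirometry and FeNO if conditions allow, and will then "enter information regarding symptoms and triggers (collected at screening) into the system". The specialist discusses the child's asthma with the caregiver, and visits 2 and 3 evaluate symptoms further. "A telemedicine visit summary will be sent to the PCP", and the study nurse reviews visit records "to assess delivery of guideline-based care". The teen section refers to "severity of child as documented within the telemedicine visits". None of these provisions sets a control score or recall window for the visits.

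**What is recorded elsewhere.** Caregiver symptom items are scheduled at baseline and at 3, 5, 7 and 12 months, and the Asthma Control Test at baseline and 7 months. Families keep a symptom diary through the school year. Medical chart and pharmacy records are reviewed at the end of the study.

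**The concern.** Randomisation protects the comparison of arms. It does not protect the path from a corrective action to later SFD, because the action is chosen by a clinician who is responding to the child. If children doing worse are stepped up more often, and children doing worse also have fewer SFD later, the model credits the poor outcome to the step-up.

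The mediation results are meant to explain how TEAM-UP works. Run as written, the model could report that specialist step-ups contribute nothing, or do harm, when they help. The direct effect would then be too large, and the benefit would seem to come from directly observed therapy (DOT) and contact alone.

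**Working it through.** The plan gives no figure for the mediation analysis, so there is none to reproduce. What follows shows the direction of the bias and how its size depends on assumptions.

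**Inputs from the plan** (Sample Size and Power Justification): SD of SFD 3.6, within-subject correlation 0.3.

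**Assumptions:** true step-up benefit 0.8 SFD; one step-up decision per child; children are uncontrolled if in the lower half of SFD at decision time; half of all children are stepped up; uncontrolled children are stepped up more often by a gap g.

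**Step 1: no covariates, as the plan is written.**
- Mean SFD of the uncontrolled and controlled halves lies 0.798 × 3.6 = 2.873 below and above the overall mean.
- Stepped-up minus other children, SFD at decision time: -2 × 2.873 × g = -5.746g.
- Carried to later SFD by the correlation: 0.3 × -5.746g = -1.724g.
- Fitted coefficient: 0.8 - 1.724g.

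| Gap g | Bias | Fitted coefficient (true 0.8) |
|---|---|---|
| 0.1 | -0.17 | 0.63 |
| 0.2 | -0.34 | 0.46 |
| 0.4 | -0.69 | 0.11 |
| 0.6 | -1.03 | -0.23 |
| 0.8 | -1.38 | -0.58 |

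Simulation of gaps of 40 to 80 points gave 0.12 to -0.59, in agreement.

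**Step 2: baseline SFD added.** Covariance of step-up with SFD at decision time is k = -0.399 × 3.6 × g = -1.436g. Given baseline, the covariance with later SFD is 0.3k - 0.09k = 0.21k, and the step-up variance is 0.25 - (0.3k)²/12.96.
- g = 0.4: k = -0.574; bias -0.1206/0.2477 = -0.49; coefficient 0.31.
- g = 0.8: k = -1.149; bias -0.2413/0.2408 = -1.00; coefficient -0.20.

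Simulation with 30%, 50% or 70% uncontrolled gave 0.52 to 0.70 for gaps of 10 to 20 points and -0.21 to 0.47 for gaps of 30 to 80 points. If step-ups follow baseline severity alone, the baseline-adjusted coefficient is 0.78 to 0.82, with no bias.

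**Step 3: control at the decision added.**
- Decisions depend only on visit-time SFD, measured without error: 0.78 to 0.82. This recovery is built into the set-up.
- Recorded counts have reliability 0.6: 0.25 to 0.75.
- Underlying severity drives decisions: -0.86 to 0.63.

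Adjustment reduced the bias in every scenario where visit status or underlying severity drives step-ups. It removed the bias only in the first.

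**Step 4: two arms.** Suppose TEAM-UP raises interview SFD by 0.8, the true direct effect is 0.80 and the true indirect effect is 0.12 to 0.31.
- Without control adjustment: indirect 0.00 to 0.26, direct 0.85 to 1.07.
- With interview control added: indirect 0.12 to 0.32, but the direct coefficient falls to 0.61 to 0.62, because control is itself affected by assignment. The drop is 0.8 × 0.3 × (1 - 0.3)/(1 - 0.09) = 0.185, and 0.80 - 0.185 = 0.615.
- Total minus indirect returns 0.80.

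**Step 5: which actions an interview can serve.** If DOT starts 0 to 4 weeks after baseline (an assumption), visit 1 falls at weeks 4 to 8, visit 2 at weeks 8 to 14 and visit 3 at weeks 12 to 20. The first interview is at week 13, so it mainly precedes visit-3 actions.

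**The case against.** The strongest reply is that little depends on this. The analysis is supportive, the documents give no step-up rule or rate, and the section on the initial visit expects many children to need a step-up because of their enrolment level. If that governs, baseline adjustment suffices. Precision is also low: with 150 TEAM-UP children the standard error of a baseline-adjusted step-up coefficient is 0.38 to 0.72, so power for an unbiased 0.8 is only about 20 to 56%, and at gaps of 10 to 20 points the bias is only 0.2 to 0.6 standard errors. The planned mediator also covers allergy and co-morbidity care, not step-ups alone. All of this stands, and it limits the weight of the point. It does not answer it, because the model as written does not name even baseline SFD.

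The plan also holds partial substitutes: the diary, chart review, the interviews, and spirometry and FeNO where conditions allow. That is right, but the plan does not say that any of them will enter the mediation model.

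A reader might infer from the screening-data sentence that specialists decide on outdated information. The documents do not support this: the specialist speaks with the caregiver, and later visits evaluate symptoms. A reader might also infer that control counts taken at the visits would repair the mediation model. They cannot enter the two-arm model, because enhanced care (EC) has no such visits. Nor would they remove the confounding, since specialists also act on examination, triggers and co-morbidities.

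**Conclusion.** The point holds for the supportive mediation analysis only. As written, the corrective-action path is open to confounding by indication, probably toward no benefit or apparent harm, provided that children doing worse are stepped up more often. The documents do not give its size. Under the stated assumptions it runs from none, when step-ups follow baseline severity and baseline SFD is in the model, to a reversed sign, when current control drives them strongly.

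It would be wrong to extend this to the trial's main result. The primary SFD comparison, safety, clinical decisions and the between-arm comparison of corrective actions do not rest on this path. The change is worth making because it is cheap, but it is optional.

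**What to change.** Add one paragraph on the mediation model:

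1. Adjust the action-to-SFD path for baseline SFD and for symptom control at the last interview dated before the action, never one after it.
2. Treat that control as affected by assignment. Take the direct effect as total minus indirect, or use a method for treatment-affected confounders. Do not read it from the control-adjusted coefficient.
3. State that actions before 3 months are adjusted for baseline only, unless diary or chart data prove usable.
4. State that adjustment reduces but does not remove the bias, because specialists act on more than symptoms and caregiver counts carry error. Report the path with its confidence interval and a sensitivity analysis for unmeasured confounding.

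This uses interviews that are already scheduled and needs no new contact with families.

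Optional addition: at each telemedicine visit, record dated prior-4-week counts of symptom days, night awakenings and rescue-use days. The nurse's fidelity review could then report TEAM-UP step-ups by control status, so that a low count due to good control can be told from missed care. With 180 children, 3 visits and an assumed 2 minutes each, the cost is 180 × 3 × 2 = 1,080 minutes, or 18 specialist hours over the trial. Decisions stay with the specialist.
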